#### COVID-related questions

Please indicated the degree to which you expect COVID-19 to impact the following events.

|  | Strongly Disagree | Disagree | Neutral | Agree | Strongly Agree |
|--|-------------------|----------|---------|-------|----------------|
| 28. I was worried that coming to the hospital for infant testing would expose me and my child to COVID-19  |                   |          |         |       |                |
| 29. Challenges with travel to and from the hospital (cost and/or availability of cars) as a result of COVID-19 caused me to delay or miss attending some postpartum appointments |                   |          |         |       |                |
| 30. I delayed or missed postpartum appointments because I was feeling unwell and did not want to risk exposing others to illness.  |                   |          |         |       |                |

#### Assessing delivery VL as intervention

Please indicate the approximate dates (month and year) that you've had a VL sample collected, the results of these tests, and the reason for the test since you became pregnant. Please leave blank for any that were not collected.

31. First test since pregnancy was confirmed
- Test one** date \_\_\_\_\_
  - Test one results (select one)
    - Detectable
    - Undetectable
    - I got the result but don't remember what it was
    - I was never informed of the result
  - Purpose of test

- i. Routine VL test
  - ii. Follow up from detectable VL
  - iii. Research
  - iv. I don't know
- 32. Second test since pregnancy was confirmed
  - a. **Test two** date \_\_\_\_\_
  - b. Test two results (select one)
    - i. Detectable
    - ii. Undetectable
    - iii. I got the result but don't remember what it was
    - iv. I was never informed of the result
  - c. Purpose of test
    - i. Routine VL test
    - ii. Follow up from detectable VL
    - iii. Research
    - iv. I don't know
- 33. Third test since pregnancy was confirmed
  - a. **Test three** date \_\_\_\_\_
  - b. Test three results (select one)
    - i. Detectable
    - ii. Undetectable
    - iii. I got the result but don't remember what it was
    - iv. I was never informed of the result
  - c. Purpose of test
    - i. Routine VL test
    - ii. Follow up from detectable VL
    - iii. Research
    - iv. I don't know
- 34. Forth test since pregnancy was confirmed
  - a. **Test four** date \_\_\_\_\_
  - b. Test four results (select one)
    - i. Detectable
    - ii. Undetectable
    - iii. I got the result but don't remember what it was
    - iv. I was never informed of the result
  - c. Purpose of test
    - i. Routine VL test
    - ii. Follow up from detectable VL
    - iii. Research
    - iv. I don't know

#### Engagement with HITSystem 2.1 - **INTERVENTION ONLY**

- 35. Since your child was born, have you received any SMS from the hospital?
  - a. No, I have not received any SMS.
  - b. Yes, I have received at least one SMS from the hospital but less than 3
  - c. Yes, I have received between 3 and 5 SMS
  - d. Yes, I have received more than 5 SMS
- 36. Have you received and SMS for any of the following reasons?
  - a. To check how you are doing.....Yes / No
  - b. To inform you of your next appointment date..... Yes / No
  - c. To remind you to take ART medications..... Yes / No
  - d. To let you know your child was due for services.....Yes / No
  - e. Asking you to return to the hospital to be informed of a test result..... Yes / No
- 37. If yes to any option in number 29, please answer question 30 regarding your reaction to receiving the text messages, otherwise skip to 31.
  - a. I did not find the SMS helpful.....True / False
  - b. I found the SMS helpful to remember to take medication.....True / False
  - c. I was worried that someone would see the SMS and discover my status .....True / False
  - d. The SMS helped me feel more connected to the hospital/my care provider.....True / False

- a. The SMS helped me remember when my appointments were.....True / False
  - b. Someone other than me read one of the SMS and asked me about it.....True / False
  - c. A family member or friend discovered my HIV status because of the SMS.....True / False
  - d. The SMS gave me important information regarding my or my infant's care.....True / False
  - e. The SMS motivated me to continue PMTCT and/or EID care.....True / False
38. Please select a preference for frequency of ART adherence messages going forward:
- a. Never, please stop sending me adherence messages
  - b. Daily
  - c. Weekly
  - d. Every two weeks
  - e. Monthly

## Appendix IID. Facility Assessment Form

Date of survey \_\_\_\_\_

Conducted by: \_\_\_\_\_

1. Facility Name \_\_\_\_\_
2. Resource level (district, county, provincial, referral, etc) \_\_\_\_\_
3. Does the hospital have an implementing partner?
  - a. If yes, who:
    - i. Afya+
    - ii. Walter Reed
    - iii. PEPFAR
    - iv. FACES
    - v. USAID
    - vi. Other, please specify \_\_\_\_\_
  - b. Please describe the primary contributions of the implementing partner, especially in regards to PMTCT, EID, or HIV services at the hospital \_\_\_\_\_

4. Please indicate the number of full time (FT) and part-time (PT) doctors, nurses, mentor mothers, or other **clinical personnel** who work primarily in each of the following departments. If one person works in multiple departments, please only indicate the **primary** place of employment to avoid double-counting personnel.

|           |    | Doctor/Clinical Officer | Nurse | Mentor Mother | Other (specify) |
|-----------|----|-------------------------|-------|---------------|-----------------|
| ANC/PMTCT | FT |                         |       |               |                 |
|           | PT |                         |       |               |                 |
| Maternity | FT |                         |       |               |                 |
|           | PT |                         |       |               |                 |
| MCH       | FT |                         |       |               |                 |
|           | PT |                         |       |               |                 |
| CCC       | FT |                         |       |               |                 |
|           | PT |                         |       |               |                 |

5. How many pharmacists are employed:
  - a. Full time \_\_\_\_\_
  - b. Part time \_\_\_\_\_
6. How many lab technicians are employed:
  - a. Full time \_\_\_\_\_
  - b. Part time \_\_\_\_\_

Please survey the last full **3 months** of paper-based registers to answer the questions 7-. For example, if this survey is being conducted in June, please survey March, April, and May.

7. How many NEW PMTCT enrollments occurred in each of the previous three months  
 3 months ago \_\_\_\_\_ 2 months ago \_\_\_\_\_ 1 month ago \_\_\_\_\_
8. How many patients total filled or refilled ART prescriptions in the previous 3 months (including male and female infants, children, adolescents and adults)  
 3 months ago \_\_\_\_\_ 2 months ago \_\_\_\_\_ 1 month ago \_\_\_\_\_
9. How many women delivered their babies in the maternity in the previous 3 months?  
 3 months ago \_\_\_\_\_ 2 months ago \_\_\_\_\_ 1 month ago \_\_\_\_\_
10. How many infants were enrolled in EID in the previous three months  
 3 months ago \_\_\_\_\_ 2 months ago \_\_\_\_\_ 1 month ago \_\_\_\_\_

## Appendix IIE. Provider Survey

### Filled by site coordinator:

Provider ID number \_\_\_\_\_

Hospital \_\_\_\_\_

Date of interview \_\_\_\_\_

### Provider Information

1. Gender.....Male / female
2. Age: \_\_\_\_\_
3. Please circle the title which best describes your role at the hospital:
  - a. Mentor mother
  - b. Nurse
  - c. Clinical officer/doctor
  - d. Laboratory technician
  - e. Data entry personnel
  - f. Administrator
  - g. Other, please specify \_\_\_\_\_
4. What department do you work in, primarily:
  - a. ANC/PMTCT
  - b. Maternity
  - c. MCH
  - d. Laboratory
  - e. CCC
  - f. Rotating departments
  - g. Other, please specify \_\_\_\_\_
5. How long have you worked in the healthcare field – at this hospital or others? \_\_\_\_\_ years

### PMTCT/VL Knowledge

6. Which best describes your level of knowledge regarding the most recent national guidelines for PMTCT and VL monitoring?
  - a. I am very familiar with these guidelines
  - b. I am somewhat familiar with these guidelines
  - c. I am somewhat unfamiliar with these guidelines
  - d. I am very unfamiliar with these guidelines
7. Identify whether each of the following statements is true or false:
  - a. Per Kenya national guidelines, an HIV+ pregnant women newly initiated on treatment should receive her first VL test 3 months after treatment is started.....True / False
  - b. Per Kenya national guidelines, an HIV+ pregnant woman previously initiated on treatment should receive her first VL test 3 months after pregnancy is confirmed.....True / False
  - c. Per Kenya national guidelines, routine VL testing during pregnancy and breastfeeding should occur every 3 months.....True / False
  - d. Per Kenya national guidelines, HIV+ pregnant women who have high VL results should receive adherence counseling and then a repeat VL test after 3 months.....True / False
8. Per Kenya national guidelines, All HIV+ pregnant women should receive a minimum of how many ANC appointments?
  - a. 2
  - b. 3
  - c. 4
  - d. 5
9. Per Kenya national guidelines, all HIV-exposed infants should receive their first HIV test at the following age:
  - a. Within 2 weeks

- b. 6 weeks
- c. 6 months
- d. 12 months
- e. At cessation of breast feeding

#### Motivation

Please indicate the degree to which you agree or disagree with each of the following statements.

SD= strongly disagree, D=disagree, N=neither agree nor disagree, A=agree, SA = strongly agree

|  | SD | D | N | A | SA |
|--|----|---|---|---|----|
| 10. I always follow national guidelines regarding PMTCT and VL monitoring for HIV+ pregnant and postpartum women.  |    |   |   |   |    |
| 11. Other hospital staff always following national guidelines regarding PMTCT and VL monitoring for HIV+ pregnant women and postpartum mothers.                                      |    |   |   |   |    |
| 12. My colleagues and I are actively trying to improve adherence to all national guidelines at the hospital level.   |    |   |   |   |    |
| 13. Following national guidelines for VL monitoring among HIV+ pregnant women/new mothers is extremely important for mom and baby's well-being                                       |    |   |   |   |    |
| 14. Sometimes, it is OK to use professional judgement to delay a VL test, even when guidelines indicate that one should be provided.   |    |   |   |   |    |
| 15. Factors outside of my control make it difficult to provide guideline-adherent PMTCT and VL services to HIV+ pregnant women.  |    |   |   |   |    |
| 16. I try to provide guideline-adherent PMTCT services (including ART initiation, VL testing, regimen changes, etc.) because colleagues and hospital administration expect it of me. |    |   |   |   |    |
| 17. Some aspects of the national guidelines are more important to adhere to than others  |    |   |   |   |    |
| 18. I rely more often on my professional instinct and/or consultation with colleagues to inform patient care than on guidelines  |    |   |   |   |    |
| 19. I believe that PMTCT/EID/VL guidelines were developed based on concrete evidence generated through rigorously conducted scientific studies.                                      |    |   |   |   |    |

For questions 20 –26, indicate the level to which you agree or disagree that each of the following are barriers to providing guideline adherent PMTCT care.

SD= strongly disagree, D=disagree, N=neither agree nor disagree, A=agree, SA = strongly agree

|     |   | SD | D | N | A | SA |
|-----|---|----|---|---|---|----|
| 20. | Colleagues and hospital administration do not always support the provision of guideline-adherent PMTCT and VL services  |    |   |   |   |    |
| 21. | Provider workload is too high to provide all recommended assessments for PMTCT.   |    |   |   |   |    |
| 22. | Guidelines are unclear and/or too complex to follow   |    |   |   |   |    |
| 23. | Mothers do not always consent and/or adhere to the guideline-adherent services that we provide  |    |   |   |   |    |
| 24. | Stock outs of supplies or drugs affect the provision of PMTCT services  |    |   |   |   |    |
| 25. | Patients are not adhering to PMTCT recommendations because they fear exposure to COVID-19.  |    |   |   |   |    |
| 26. | Hospital level protocol changes in response to COVID-19 (e.g. longer drug dispensing intervals, recommendations to limit patient exposure, etc) prevents me and my colleagues from providing PMTCT care as recommended by the national guidelines |    |   |   |   |    |

27. Please describe any other barriers to providing guideline-adherent PMTCT care \_\_\_\_\_

Interaction with HITSystem 2.1 (Intervention sites & End-of-Study, only)

28. On average, how many hours **per week** do you use the HITSystem?

- a. <1 hour
- b. 1-3 hours
- c. 3-5 hours
- d. 5-10 hours
- e. >10 hours

29. On average, how many days **per week** do you log in to the HITSystem?

- a. 1 days
- b. 2 days
- c. 3 days
- d. 4 days
- e. 5+ days

30. In the **past month**, have you logged into the HITSystem for any of the following reasons?

- a. To enter a new patient entry.....yes / no
- b. To update data on an existing patient entry.....yes / no
- c. To use alerts to identify patients who have missed services.....yes / no
- d. To check a patient's test result.....yes / no
- e. To find patient tracing information..... yes / no
- f. To access Kenya's national PMTCT/EID/VL guidelines.....yes / no
- g. To generate a report of review facility-level outcomes and data.....yes / no

31. Please rank each of the following HITSystem components by their level of usefulness to you, with 1 being the most useful and 5 being the least useful

- a. Patient tracking \_\_\_\_\_
- b. Accessing guidelines \_\_\_\_\_
- c. Generating reports \_\_\_\_\_
- d. Checking a lab result \_\_\_\_\_
- e. Locating a patient's clinical record \_\_\_\_\_

32. Briefly describe any challenges you experienced implementing HITSystem \_\_\_\_\_

---

---

---

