### **(b) Study Population**

The primary target population for the study is HIV-positive pregnant women.

**Inclusion criteria for HIV-positive pregnant women:** All HIV-positive women presenting for PMTCT services at study hospitals during pregnancy will be eligible for enrollment in the proposed study. Pregnant women under the age of 18 are eligible for inclusion in this study. Since Kenyan law allows pregnant women the same capacity to consent as an adult, young women under the age of 18 will be able to provide consent for themselves. Mentor mothers will take additional time with young women to ensure comprehension, emphasizing that participation is optional and not a requirement for receiving standard PMTCT/EID services for themselves or their infant.

Participants who do not own a mobile phone are also eligible for study enrollment. Investigators will not provide mobile phones to women but, rather, will evaluate the efficacy of the intervention's other components (alerts to provider for missed services) among participants without phones. Mobile phone ownership will be assessed as a mediator/moderator of intervention effectiveness.

**Exclusion criteria for HIV-positive pregnant women:** HIV-positive pregnant women will be excluded from study participation if she has any condition (including drug abuse, alcohol abuse, or psychiatric disorder) that study or hospital staff feel precludes her from providing informed consent. Capacity will be determined at the time of consent. Additionally, women who transfer care from one study site to another during their PMTCT services will be ineligible for enrollment at their new facility.

To assess mediators and moderators of HITSystem effectiveness, as well as part of the objective 4 evaluation of facility adoption, we will also interview providers at intervention and control hospitals.

**Inclusion criteria for providers:** Providers will be eligible to complete the survey if they (1) work primarily in ANC, PMTCT, CCC, laboratory, or MCH departments, (2) will have been involved in the provision of PMTCT care during the course of the study, and (3) have interacted with the HITSystem 2.1 during the course of the study (intervention sites, only).

**Exclusion criteria for providers:** Providers will be excluded from survey eligibility if they do not provide informed consent.

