## Procedures and Data Management

**Staffing and responsibilities.** We will hire and train one full time mentor mother for each study hospital. Each mentor mother will be trained to conduct study procedures specific to the study arm allocation. At all sites, mentor mothers will assess eligibility, conduct informed consent procedures and surveys, and facilitate VL testing at the time of delivery and by 6 months postpartum if not retested prior. At sites implementing HITSystem 2.1, mentor mothers will be the primary persons to enter and routinely update patient data. Mentor mothers also will lead patient outreach and follow-up efforts (phone or texting via HITSystem 2.1) and coordinate with community health workers (CHW) for targeted physical tracking if needed for VL testing at research-specific time points. Site Coordinators will routinely visit each study hospital to provide supportive supervision to ensure adherence to study protocols.

**Description of procedure and data collection:** At sites implementing HITSystem 2.1, all patient-specific data including: infant and maternal demographics; women's phone number and patient tracing information; women's appointment attendance and ART medication refills/pill counts; infant's date of birth, birth weight, and gestational age at delivery; dates of maternal VL sample collection, test processing, results return, and notification; and maternal VL results will be entered directly into HITSystem 2.1. ART adherence will be measured by pill counts collected at each consultation via HITSystem 2.1. At SOC sites, all clinical and PMTCT service related data will be collected in the existing paper-based registries by health care providers as part of routine services. Because routine pill counts for ART adherence are well outside of SOC practice and could modify behaviors in the control arm, we will rely on pharmacy refill records and chart review for any provider notes related to adherence. During their monthly site visits, site coordinators will review hospital registries at SOC sites to document patients' PMTCT engagement in study logs.

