**Effectiveness:** Objectives 1 & 2 assessing complete PMTCT retention and viral suppression will evaluate effectiveness. We will also measure adverse outcomes as a result of the program.

**Adoption:** At the *facility-level*, we will note any facilities which decline study participation and reasons for refusal. Among participating hospitals, the facility assessment form – filled out pre-mid-post study implementation – will collect data regarding resource level, patient-provider ratios, annual volume, implementing partners and outside support, and other facility details will be used to assess representativeness with Kenyan health care facilities. At the *provider-level*, adoption will be evaluated through provider surveys, assess the degree to which providers used HITSystem 2.1, determine which components were most beneficial, and assess facilitators and barriers to HITSystem 2.1 adoption. *Patient surveys* will similarly assess utility of SMS outreach components and suggestions to optimize benefit.

**Implementation:** Any changes to HITSystem 2.1 programming or study protocols will documented in research logs and/or through IRB amendments. Any changes to HITSystem 2.1 implementation at the hospital-level (i.e. location changes of desktop to better suit workflow, changes in key users, etc) will also be documented in study logs to guide implementation recommendations. We will review all HITSystem texting logs during the implementation period to assess fidelity of the SMS component by calculating the proportion of SMS sent according to participant preference (correct frequency and content) and the proportion received by a functioning mobile number. We will compare this with participants' reports of the number of SMS received as part of the study and the reasons for these SMS, which will be collected as part of the patient surveys.

**Maintenance:** Continued HITSystem 2.1 enrollment after the study enrollment period has ended (years 3-5) and utilization after the study follow up period (year 4-5) will serve as an indicator of system maintenance. In Years 3-5, the US-based study manager will compare the overall number of HITSystem 2.1 enrolments with PMTCT registers to assess if reach is being maintained. Using the HITSystem 2.1-generated alerts report, s/he will document the number and duration of provider alerts as a measure of system use.

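### Provider survey item 29 has no answer below one login day a week, so its login frequency can err only upward

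*Combined protocol and SAP*

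**What the plan says.** The Adoption paragraph of the Objective 3 methods says that, at provider level, "adoption will be evaluated through provider surveys, assess the degree to which providers used HITSystem 2.1". Table 7 lists system use among the adoption measures and gives facility assessment forms, provider surveys and patient surveys as the sources. The Objective 3 analysis of survey data is descriptive: proportions, medians and means.

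The questions on use are items 28 to 32 of Appendix IIE, asked only at intervention sites and only at the end of the study:

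- Item 28, hours of use per week: under 1, 1-3, 3-5, 5-10, over 10.
- Item 29, days per week "do you log in to the HITSystem": 1, 2, 3, 4, 5 or more.
- Item 30, past month: "have you logged into the HITSystem for any of the following reasons", followed by seven purposes, each yes or no.
- Items 31 and 32: a ranking of components by usefulness, and free text on challenges.

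Section 5.0(b) admits intervention-site providers who, besides working in a relevant department and taking part in PMTCT care, "have interacted with the HITSystem 2.1 during the course of the study". It sets no minimum amount or recency of use. Section 5.0(c) samples providers purposively across departments and roles. The Provider surveys paragraph expects 5 providers per site, 30 of them at intervention sites.

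**The concern.** A login-frequency question that starts at one day a week cannot describe anyone who logs in less often than that. The form gives no instruction for such a respondent, so she either overstates her use or leaves the item blank. Both responses push the summary the same way: the first moves her up to weekly use, and the second removes her from the denominator.

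The design makes such respondents plausible. One interaction during the study is enough to qualify, staff are drawn from laboratory, CCC and MCH as well as antenatal care, and the form itself allows for rotating staff. At intervention sites, "mentor mothers will be the primary persons to enter and routinely update patient data", so other staff may well log in only now and then.

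At stake is one descriptive implementation measure: how often providers at intervention sites used the system. Because the items are asked once, at the end, no second measurement could correct it.

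**Working it through.** The plan states no figure for login frequency, so there is none to reproduce. The check compares the answer scale with the people who may answer it, and then sizes the effect under stated assumptions.

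**Who can answer, and where they land**

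| Provider at end of study | Eligible? | Item 28 | Item 29 | Item 30 |
|---|---|---|---|---|
| Never used the system | No | - | - | - |
| Used it once, or has stopped | Yes | Under 1 hour (accurate but pooled) | 1 day (false) or blank | Can answer no to all seven |
| Logs in about once a month | Yes | Under 1 hour (accurate but pooled) | 1 day (false) or blank | Some yes, as a weekly user would answer |
| Logs in one day a week, briefly | Yes | Under 1 hour | 1 day (true) | Some yes |

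Rows two and three have no truthful answer on item 29. Item 30 can separate row two from row four. Nothing on the form separates row three from row four.

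**Effect on the proportion using the system weekly**

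Inputs: 5 providers x 6 intervention sites = 30. Let k be the number who log in less than weekly. The documents do not give k, so a range is shown.

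- True share logging in at least weekly = (30 - k)/30.
- Recorded share if all k tick the lowest answer = 30/30 = 100%.
- Overstatement = k/30, which is 1/30 = 3.3 percentage points per provider.
- If all k leave the item blank, the share among those answering is (30 - k)/(30 - k) = 100%, the same result.

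| k (assumed) | True weekly share | Recorded among answerers | Overstatement |
|---|---|---|---|
| 3 | 90% | 100% | 10 points |
| 6 | 80% | 100% | 20 points |
| 10 | 67% | 100% | 33 points |

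**Effect on the mean and median**

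A provider whose true figure is d days (0 <= d < 1) and who ticks 1 day adds (1 - d)/30 to the mean. The total is at most k/30 day: 0.10, 0.20 and 0.33 day for k = 3, 6 and 10.

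As an illustration, assume k = 6, d = 0.25 and 3 days for the other 24:

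- True mean = (24 x 3 + 6 x 0.25)/30 = 73.5/30 = 2.45 days.
- If the six tick 1 day: (72 + 6)/30 = 2.60 days.
- If the six leave it blank: 72/24 = 3.00 days among those answering.

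The median does not move if the below-weekly users tick the lowest answer and number fewer than half of the 30.

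**A comparison within the plan's own forms**

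The patient questions on SMS received (Appendices IIB and IIC) begin with an answer for having received none. Item 29 lacks the equivalent.

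**Item 28**

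Its lowest band is open at zero, so it forces nobody upward. It does not distinguish no use from brief use, and exactly 3 or 5 hours fits two bands.

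**The case against.** The best defence is that item 29 is not the whole measure. Item 28 gives a rare user an accurate answer. Item 30, directly below item 29, lets a lapsed user answer no to every purpose. Item 32 invites comment. Adoption also covers component benefit, facilitators and barriers. Elsewhere in the Objective 3 methods, enrolments are compared with PMTCT registers, and the number and duration of alerts serve as a measure of system use. The objective is descriptive and not powered, and about 30 purposively chosen providers would not estimate facility-wide use even with a perfect scale.

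Most of this stands, and it limits the point. It does not remove it. No rule links item 30 to item 29, and item 30 cannot tell monthly from weekly users. The register and alert measures are facility-level and do not show how often individual providers log in. Table 7 names no login record as a source for adoption.

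A reader might go further and infer that Objective 3 will report near-universal weekly adoption, and that a ministry would judge roll-out on it. The documents do not support that. Nowhere is adoption defined as the share logging in at least weekly, and the Abstract and section 9.0 tie dissemination to efficacy and cost-effectiveness. A reader might also infer that both use items force respondents into weekly use; item 28 does not.

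**Conclusion.** The point holds for item 29. Eligible providers who log in less than weekly, or no longer log in, can only be recorded at one day a week or go missing, so the login-frequency result can err in one direction only. The size is 3.3 percentage points of apparent weekly use for each such provider among about 30 who ticks the lowest answer, and at most 1/30 day on the mean. The total depends on how many such providers are surveyed, which the documents do not say; the values of k above are assumptions.

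Item 28 has a lesser fault of pooling and overlapping bands. That adoption as a whole is overstated does not follow, since other items and sources also describe it. Neither complete PMTCT retention nor viral suppression is touched. It is a small defect, worth correcting because the correction is nearly free.

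**What to change.** In item 29, put two answers before 1 day: *I do not currently log in* and *less than one day a week*. In item 28, add *none* and make the bands exclusive: none; under 1; 1 to under 3; 3 to under 5; 5 to under 10; 10 or more.

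Report the full item 29 distribution among all intervention-site providers surveyed, with the number of blanks shown. Check each blank against items 28 and 30. Do not count blanks automatically as non-users, because that would misclassify ordinary item non-response.

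If the survey has already been given, report item 29 only alongside items 28 and 30, and state that its lowest category may include less-than-weekly users.

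The cost is a few words on one form that exists only in English and whose HITSystem items are used once. No extra visits, staff or participants are needed.
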